It is anticipated that the case mix in this study will be approximately 70% low risk/ 30% intermediate prognosis cases, leading to a predicted CyberKnife monotherapy 94% 5 year PSA DFS rate, with a potential range of 82% (0% favorable or low risk prognosis cases accrued) to 98% (100% favorable cases accrued). If the protocol case mix deviates from these percentages, then the protocol DFS rate required to successfully test the primary efficacy hypothesis detailed in Section 2.0 may need to be adjusted accordingly.

Table 2. Toxicity review for HDR-Monotherapy for Prostate Cancer

				>= Gd 3 toxicity	•	
HDR Details	Institution	# pts	Median f/u	Total (%)	GI (%)	GU (%)
6-7.25Gy x 6	CA Endocurie ¹⁸	117	3.3	3	0	3
9.5Gy x 4	Beaumont ¹⁹	95	4.2	8	0	8
7.5Gy x 6	Texas Tech ²⁰	145	5	5-8*	1	4 – 7*
6.5Gy x 6	Gamma West (SLC) ²¹	328	1.2	1	0	1
6Gy x 8-9	Osaka (Japan) ²²	111	2.25	7	1	6
	Totals	796	2.4	6	0 -1	5

^{*3%} acute and 4% chronic grade 3 GU toxicity – It is unclear to what degree acute and chronic grade 3 GU toxicity populations overlap in this study.

Due to short median follow-up, the incidence of >= grade 3 late toxicity is likely underestimated. We project that the incidence of late toxicity will increase by approximately 50% when all data reach 5 years maturity, yielding a projected cumulative 5 year HDR monotherapy grade 3 toxicity incidence of 9% (7-8% GU; 1-2% GI). In this study, biochemical disease-free survival (ASTRO and Phoenix definition), freedom from local recurrence, freedom from distant relapse, clinical disease-free survival, disease-specific survival and overall survival will be recorded. The incidence of grade 3 or higher toxicity and the effect of CyberKnife® radiosurgery on bladder, bowel, and sexual function will be followed and monitored using standardized, patient self-administered questionnaires and compared with results published in peer-reviewed literature for other prostate cancer therapeutic modalities. 17

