We chose N large enough to test the null hypothesis against the alternative hypothesis with power equal to 80% at the one-sided 5% significance level.

Let Z_u denote the upper u-th percentile of the standard normal distribution. Hence $Z_{.05} = 1.645$ corresponding to the one-sided 5% level of significance and $Z_{.20} = 0.84$ corresponds to 80% power. Then the sample size is determined by Formula 1:

$$N = \frac{\left[z_{\beta}\sqrt{\pi_{1}(1-\pi_{1})} + z_{\alpha}\sqrt{\pi_{0}(1-\pi_{0})}\right]^{2}}{\left[\pi_{1} - \pi_{0}\right]^{2}}, \text{ where}$$

 π_1 is the expected proportion of CyberKnife treated patients bDFS at 5 years if the alternative hypothesis is true; the bDFS rate is then expected to equal or exceed 0.94. For purposes of sample size estimation, we require 80% power if $\pi_1 \geq 0.945$. π_0 is the expected lower limit of the 95% confidence interval for π and is set equal to 0.90. Then N= 232. Allowing 8% sample size degradation for lost to follow-up, the sample size must be increased to 232/.92 = 253 subjects.

Primary Safety Objective

The primary safety objective is to establish with 95% confidence that the percentage of CyberKnife treated patients experiencing \geq Grade 3 toxicity is not more than 5% higher than the approximately 9% 5-year rate extrapolated from Table 2, Section 1.15.

With N=232 CyberKnife treated subjects, if the observed \geq Grade 3 toxicity rate equals 9%, then with 95% confidence the "true" rate \leq 12.6%. Since the difference between 12.6% and 9% is less than 5%, the sample size of 232 subjects is more than large enough to meet the primary safety objective.

11.3.1 ACCRUAL RATE: the initial three months while institutions are obtaining IRB approval, therefore we do not expect to meet the targeted monthly accrual rate until after the first three months. The estimated accrual rate is 2 patients per study site per month. Expectations of 5 treating study sites assumes an accrual period of approximately 29 months total.

11.4STATISTICAL METHODS

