11.4.1 PRIMARY OBJECTIVES

1. Efficacy

The lower limit of a one-sided 95% confidence interval for the expected proportion of patients experiencing biochemical disease-free survival (bDFS) is estimated by L, where

$$L = \frac{(2np + Z_{0.05}^2) - Z_{0.05}\sqrt{Z_{0.05}^2 + 4pn(1-p)}}{2(n + Z_{0.05}^2)}$$

Here "p" is the observed proportion of patients experiencing bDFS in either arm of the trial. The CyberKnife intervention will be considered to be effective if this study's result verifies that L is not below 90%.

2. Safety

The upper limit of a one-sided 95% confidence interval for the expected proportion of patients experiencing \geq Grade 3 gastrointestinal and genitourinary toxicity is estimated by U, where

$$U = \frac{(2np + Z_{0.05}^2) + Z_{0.05}\sqrt{Z_{0.05}^2 + 4pn(1-p)}}{2(n + Z_{0.05}^2)}$$

Here "p" is the observed proportion of patients experiencing ≥ Grade 3 gastrointestinal or genitourinary toxicity. The CyberKnife intervention will be considered to be safe if this study's result verifies that U is not more than 5% higher than the literature rate of 9%...

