- 12.5. Below are criteria for early termination of the trial (through 25%,50% and 75% enrollment of 232 patients) should an excessive number of patients experience ≥ Grade 3 gastrointestinal and genitourinary toxicity. This depends upon the number so far enrolled and a criterion that identifies too high a rate. The stopping criteria differ after 58, 116 and 174 patients have been enrolled .Consistent with Section 1.1.5, 2.0 we define an observed ≥ Grade 3 gastrointestinal and genitourinary toxicity rate of over 14% as too high. The statistical requirement is that for up to "m" patients enrolled, the number of observed cases with ≥ Grade 3 toxicity must be few enough so that there is a 95% chance that the "true" rate does not exceed 14%.

≥ Grade 3 toxicity Stopping Criteria				
Participants to	Stop study if the number of patients with grade 3-5 toxicity			
be enrolled: 253	equals or exceeds:			
	Enrollment 1-58: 4 Events			
	Enrollment 1-116: 10 Events			
	Enrollment 1-178: 17 Events			

Page 27 of 52

Regulatory Reporting: Any reports regarding safety issues and potential safety issues will also be provided to Accuray's Regulatory Affairs Department. Such reports will be evaluated and reported to the FDA and all applicable regulatory agencies, as deemed required.

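### Section 11.3 calls 232 patients ample for the safety objective, but if true toxicity equals the 9% benchmark, 232 patients meet the criterion only about 73% of the time

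*Combined protocol and SAP*

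**What the plan says.** Section 2 makes the measurement of grade 3-5 gastrointestinal and genitourinary toxicity a second primary goal. Section 1.15 projects the comparator rate from the HDR literature, "yielding a projected cumulative 5 year HDR monotherapy grade 3 toxicity incidence of 9" percent.

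Section 11.3 sets the objective: to establish with 95% confidence that grade 3 or higher "toxicity is not more than 5% higher than the approximately 9% 5-year rate extrapolated from Table 2, Section 1.15". Section 11.4.1 turns this into a decision rule based on a one-sided 95% upper limit U, for which it gives a formula. The treatment counts as safe if that limit "is not more than 5% higher than the literature rate of 9" percent. Section 12.5 confirms that the margin is in percentage points, because it labels a "gastrointestinal and genitourinary toxicity rate of over 14% as too high".

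The sample size argument in section 11.3 opens "With N=232 CyberKnife treated subjects, if the observed" rate is 9%, obtains an upper limit of 12.6%, notes that this is less than 5 points above 9%, and concludes that "the sample size of 232 subjects is more than large enough to meet the primary safety objective". The 80% power in section 11.3 belongs to the efficacy hypothesis. No power or probability of success is given for safety.

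**The concern.** The upper limit depends on the rate that the trial happens to observe. Fixing that rate at its benchmark value shows that the trial would pass if the result fell exactly there. It does not show how often the result would fall low enough to pass. When the true rate is 9%, roughly half of all possible results lie above 9%, and what matters is how much room there is before U crosses 14%.

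There is little room. The pass/fail line is just under one percentage point above the benchmark, so a treatment no more toxic than the benchmark could miss a primary criterion fairly often. A reader who had been told that the sample size was ample might then put the miss down to the treatment and not to chance.

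**Working it through.** **Inputs.** n = 232, reference rate 9% and margin 5 points (section 11.3); threshold 9% + 5% = 14% (section 11.4.1, consistent with section 12.5); one-sided Z = 1.645 and the formula for U (section 11.4.1); 253 enrolled (section 11.3); 260 subjects (section 11.2).

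**Step 1: reproduce the plan's figure.** U = [(2np + Z²) + Z√(Z² + 4np(1−p))] / [2(n + Z²)]. With n = 232 and p = 0.09, np = 20.88 and Z² = 2.706:

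- first term: 41.76 + 2.706 = 44.466
- second term: 1.645 × √(2.706 + 76.003) = 14.594
- denominator: 2 × 234.706 = 469.412
- U = 59.060 / 469.412 = 12.58%

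This agrees with the stated 12.6%. The nearest whole count, 21/232, gives 12.64%.

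**Step 2: find the cut-off.** In the same formula with n = 232, 23 events (9.9%) give U = 13.6%, which passes. With 24 events (10.3%), U = 14.1%, which fails. The rule is therefore 23 or fewer events. An exact (Clopper-Pearson) limit gives the same cut-off.

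**Step 3: probability of passing.** This is the binomial probability of a count at or below the cut-off:

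| n | Cut-off | True 8% | True 9% | True 10% |
|---|---|---|---|---|
| 232 | 23 | 88.2% | 73.3% | 53.8% |
| 253 | 26 | 92.2% | 79.7% | 60.9% |
| 260 | 27 | 93.3% | 81.5% | 63.1% |

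At n = 232 the probability rises to 96% at a true 7% and 99% at a true 6%. At a true 14% it is 4.0%, so the rule controls its false-pass rate as intended.

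**Step 4: apply the plan's own sizing formula.** Formula 1 in section 11.3 reproduces the efficacy size (231.7, so 232). For safety, with π₁ = 0.09, π₀ = 0.14 and 80% power:

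N = [0.84√(0.09 × 0.91) + 1.645√(0.14 × 0.86)]² / 0.05² = (0.2404 + 0.5708)² / 0.0025 ≈ 263.2, so about 264 evaluable patients.

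The exact binomial calculation first reaches 80% at N = 242. Because the count is discrete, it stays at or above 80% only from N = 275.

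**The case against.** **The 12.6% is right.** Step 1 confirms it, so there is no slip in the arithmetic. The fault lies in what is concluded from the figure.

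**The plan never assumes a true rate of 9%.** This stands. A reader might infer that 9% is the planning value, but section 11.3 uses it as a literature benchmark and as an illustrative observed rate. Some text points lower: section 1.13 reports no grade 3 or 4 toxicity in 26 patients, though in a small series on a different dose schedule, and section 14.5 lists reduced toxicity as a possible benefit. At a true 8% or less, 232 patients do well. Even so, section 1.15 aims at clinical equivalence with HDR in toxicity, and the plan offers no lower value. The case of a true 9% is therefore a fair one to examine, but as a scenario.

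**More than 232 may count.** This also stands. Section 11.4.1 does not fix n for the safety limit, and the 8% allowance for loss was made in the efficacy derivation. With 253 or 260 patients the probability is about 80% or 82%, in line with the efficacy target. That is adequate by the plan's own standard, but it is not a surplus, and the sentence at issue names 232.

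**The argument is about precision.** Section 2 speaks of measuring the rates accurately, and a limit 3.6 points above the estimate is reasonable precision. This would answer the point if estimation were the only aim. Section 11.4.1, however, uses the limit to decide whether the intervention is considered safe, so the chance of passing matters.

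**The figures above ignore the stopping table.** This is correct. Section 12.5 sets limits of 4, 10 and 17 events during enrolment. If those limits were binding and every event were known at each look, the chance of both continuing and passing at a true 9% with 232 patients would be about 16%. That is an illustration only, since toxicity accrues over five years and many events would come after the looks. The limits can only lower the 73%.

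**Conclusion.** The claim that 232 is more than enough is not supported. Under the plan's own rule, formula and margin, 232 patients pass about 73% of the time if the true rate equals the 9% benchmark, so such a treatment would miss the criterion about one time in four. That falls short of the 80% set for the other primary objective, for which Formula 1 would ask for about 264. With 253 or 260 patients in the denominator, the miss rate is about one in five.

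These figures rest on three assumptions: the margin is absolute, all patients in the denominator have a known toxicity outcome, and the stopping limits in section 12.5 are set aside.

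Two stronger readings are tempting, and the documents support neither. One is that the trial is too small for safety and must enrol more. The plan states no power requirement for safety, and at 253 or more, or at a true rate of 8% or below, the probability is about 80% or higher. The other is that a miss would be declared a safety signal. Section 11.4.1 says when the intervention is considered safe and is silent on what failure means.

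**What to change.** In section 11.3, delete the claim that the size is more than large enough. In its place, name the number of patients that will form the safety denominator, the largest event count that meets the criterion, and the probability of meeting it at true rates of, for example, 8%, 9% and 10%. If the denominator is 232, those entries are 23 events and 88%, 73% and 54%. If it is 253 or 260, use the corresponding rows of the table in the working.

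Add that these probabilities do not account for the toxicity stopping limits in section 12.5, which can only reduce them. The 12.6% can stay if it is described as the precision obtained at an observed 9%.

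The cost is a sentence or two. No patients are added, and no endpoint, threshold or analysis changes. The drawback is that the stated figure becomes less favourable.

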11.4.1 PRIMARY OBJECTIVES

1. Efficacy

The lower limit of a one-sided 95% confidence interval for the expected proportion of patients experiencing biochemical disease-free survival (bDFS) is estimated by L, where

$$L = \frac{(2np + Z_{0.05}^2) - Z_{0.05}\sqrt{Z_{0.05}^2 + 4pn(1-p)}}{2(n + Z_{0.05}^2)}$$

Here "p" is the observed proportion of patients experiencing bDFS in either arm of the trial. The CyberKnife intervention will be considered to be effective if this study's result verifies that L is not below 90%.

2. Safety

The upper limit of a one-sided 95% confidence interval for the expected proportion of patients experiencing \geq Grade 3 gastrointestinal and genitourinary toxicity is estimated by U, where

$$U = \frac{(2np + Z_{0.05}^2) + Z_{0.05}\sqrt{Z_{0.05}^2 + 4pn(1-p)}}{2(n + Z_{0.05}^2)}$$

Here "p" is the observed proportion of patients experiencing ≥ Grade 3 gastrointestinal or genitourinary toxicity. The CyberKnife intervention will be considered to be safe if this study's result verifies that U is not more than 5% higher than the literature rate of 9%...

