- 6.2. PATIENT REGISTRATION: Patients may be registered only after all eligibility criteria are met: see Eligibility Checklist above, and Inclusion Criteria and Exclusion Criteria CRFs (Case Report Forms). After the patient signs the Consent Form the patient is enrolled in the study, and scheduled for treatment. The pre-treatment CRFs are then filled out by the investigator and/or research assistant. This data is retained in the patient's chart and in research office. The date of registration shall be the date the consent was signed. Fiducials must be placed within 60 days, and the first fraction of radiosurgery must be administered within 90 days of registrations.

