9.3. QUALITY OF LIFE ASSESSMENTS

- 9.3.1. SF-12: The SHORT FORM-12 Health Survey measures generic health status relevant across different age, disease, and treatment groups. It provides a comprehensive, psychometrically sound assessment of health status from the patient's point of view by scoring responses to standard questions. The SF-12 is self-administered, and can usually be completed in less than 3 minutes without assistance.
- 9.3.2. EXPANDED PROSTATE CANCER INDEX COMPOSITE (EPIC)-26: is a validated comprehensive instrument developed to assess patient function and bother after prostate cancer treatment. It was developed by an expert panel of urological oncologists, radiation oncologists (including those with brachytherapy expertise), survey researchers, and prostate cancer nurses, to address symptoms related to radical prostatectomy, external beam radiotherapy, prostate brachytherapy, and hormonal symptoms. See appendix VI.
- 9.3.3. AMERICAN UROLOGICAL ASSOCIATION (AUA) SYMPTOM INDEX: Also known as the International Prostate Symptom Score (IPSS), this widely used index assesses urinary symptom bother. See appendix VI.
- 9.3.4. SEXUAL HEALTH INVENTORY FOR MEN (SHIM): is a widely used, internationally validated and sensitive instrument for assessing erectile dysfunction¹.
- 9.3.5. UTILIZATION OF SEXUAL MEDICATIONS/DEVISES: provides context for interpreting the sexual domain score of the EPIC questionnaire.
- 9.4. CRITERIA FOR DISEASE CONTROL: intervals will be measured from enrollment date.
 - 9.4.1. BIOCHEMICIAL DISEASE-FREE SURVIVAL (bDFS): is measured as time to PSA failure. While earlier reports of prostate cancer patients treated with radiotherapy have used the ASTRO consensus definition (ACD) of PSA failure, recent studies^{2,3,4} have suggested the "nadir+2" definition is a more sensitive and specific definition of biochemical failure. Indeed, a recent expert panel met in Phoenix⁵ and developed a consensus recommendation using the later definition. So that comparisons can be made with earlier literature, both definitions shall be used:

П

- 9.4.1.1.Phoenix definition: failure occurs when the PSA is 2 ng/ml more than the lowest PSA measurement before the current one, with no backdating. Administration of salvage therapy (hormones, surgery, etc...) will be considered failure.

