- 9.4.1.2.Strict ASTRO Consensus Definition (ACD): failure is defined as three consecutive rises in post-treatment PSA, measured at the specified follow-up intervals. If three consecutive PSA rises occur during the first 2 years after treatment, followed by a non-hormonal induced PSA decline, this will not be considered a failure. Administration of salvage therapy (hormones, surgery, etc...) will be considered failure. Failure date is the midpoint between the dates of the last non-rising PSA and the first PSA rise.

9.4.2. CRITERIA FOR LOCAL FAILURE:.

Clinical evidence of local progression or recurrence: Clinical failure includes a palpable abnormality that has increased in size, failure of regression of a palpable abnormality by 2 years after treatment, or redevelopment of a prostate abnormality after complete response. Patients with a prostate abnormality compatible with local recurrence, or a PSA failure shall undergo a prostate biopsy. Histologic criteria for local failure is a positive prostate biopsy more than 2 years after treatment. Patients with a normal exam and no evidence of PSA failure shall be considered controlled locally. Patients with clinical failure and no biopsy are considered local failures. If a patient is locally controlled at the time of orchiectomy or androgen ablation, he is censored and considered "not evaluable" for further local control.

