11. STATISTICAL CONSIDERATIONS

- 11.1. OVERVIEW: The study's primary goals are to determine CyberKnife monotherapy efficacy and to evaluate the incidence of grade 3 or higher toxicity as stated in Section 2.0. Per RTOG/ECOG, acute toxicity will be defined as occurring within 90 days from completion of treatment. Late toxicity will be defined as occurring more than 90 days from completion of treatment. It is graded based upon Common Terminology Criteria for Adverse Events (CTCAE), v3.0., and RTOG/ECOG definitions (see appendix 5).
- 11.2. INTERIM ANALYSIS: An interim analysis was performed. The results below are based on an overall one-sided alpha of 0.05 and using the O'Brien-Fleming spendingfunction, and were calculated using nTerim (Statistical Solutions Ltd). The interim analysis is based on 4,512 months of follow-up, out of a total possible of 15,600 months (60 months* 260 Subjects). Hence the interim analysis is performed with approximately 29% of the total data possible for the final analysis. The final alpha must now be 0.04999. If the Z-score at the interim analysis exceeds 3.45701, then the trial could be stopped. If th Z-score doesn't exceed 3.45701, then the trial will continue through the primary assessment period of 5 years, where the P-value for success is at most .0499991.

	Look 1	Final Analysis- Look 2
proportion of information	0.29	1.0
Z-Score Boudary	3.45701	1.64575
Nominal Alpha	0.00027	0.049991
Incremental Alpha	0.00027	0.05

11.3. SAMPLE SIZE:

Primary Efficacy Endpoint and Hypothesis: 5-Year Biochemical Disease-Free Survival(bDFS) Among CyberKnife Treated Patients

bDFS is the primary efficacy outcome for the study. The proportion of patients disease-free within 5 years of the initial procedure is the rate of interest. The null and alternative hypotheses are as follows:

$$H_0: \pi < 90\%$$

 $H_1: \pi \ge 90\%$

 π • • is the expected proportion of CyberKnife treated patients bDFS at 5 years. The CyberKnife procedure is considered to be effective if this study's result verifies that the lower limit of the one-sided 95% confidence interval for π is not below 90%. Statistical Sample Size Derivation

Primary Efficacy Objective

We calculate the CyberKnife Treatment Group sample size, N, required to test the null hypothesis that the rate in the Treatment Group is less than 90%, against the one-sided alternative hypothesis that the rate is at least 90%...

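### Section 11.4.1 tests 5-year bDFS as a crude proportion without saying how patients lost, withdrawn or dead without PSA failure are counted, and sections 9.4 and 11.3 start the 5 years on different dates

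*Combined protocol and SAP*

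**What the plan says.** Section 9.4.1 says bDFS "is measured as time to PSA failure", with salvage therapy also counted as failure. Death is not mentioned there; it appears in 9.4.3.2, for a different endpoint (disease-free survival).

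Section 11.3 sets the target: "The proportion of patients disease-free within 5 years of the initial procedure is the rate of interest". It describes π as a quantity that "is the expected proportion of CyberKnife treated patients bDFS at 5 years". On numbers it says: "Allowing 8% sample size degradation for lost to follow-up, the sample size must be increased to 232/.92 = 253 subjects".

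Section 11.4.1 estimates π by a crude p, which "is the observed proportion of patients experiencing bDFS in either arm of the trial". (The trial has one arm.) The Wilson limit L must not be below 90%. Kaplan-Meier curves appear only in 11.4.2, as descriptive output. The only explicit censoring rule, in 9.4.2, concerns local control. Section 14.6 lets patients leave at any time and says only that they may be asked to continue PSA tests.

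On the clock, section 9.4 says "intervals will be measured from enrollment date". Section 6.2 says "After the patient signs the Consent Form the patient is enrolled in the study", dates registration at consent and allows up to 90 days to the first fraction. Section 11.3 counts from the procedure. The visit table and 9.1.4 schedule PSA in months after therapy, every 6 months from month 6 to year 5.

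**The concern.** A crude x/n equals the 5-year rate only if every patient's 5-year status is known. The plan itself expects 8% loss, and some men may die without PSA failure. Each such patient must be left out, counted as a success, counted as a failure or censored, and the plan does not choose. In a single-arm trial judged against a fixed 90%, no control group offsets that choice. If it is made once the data are known, the stated level and power are no longer guaranteed.

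The conflicting start dates add a second opening. If 60 months run from enrollment, the visit scheduled 60 months after therapy can fall outside the period, and failures found there are missed.

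**Working it through.** **Inputs.** From section 11.3: π0 = 0.90, π1 = 0.945, one-sided 5%, z values 1.645 and 0.84, 8% loss. From 11.4.1: the Wilson limit. From 6.2: the 90-day maximum. Assumed: constant hazards, and loss and death unrelated to PSA failure. The documents give no death rate, so 3%, 5% and 10% are used as a range.

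**The plan's own figures.** Formula 1: [0.84·√(0.945·0.055) + 1.645·√(0.90·0.10)]² / 0.045² = (0.1915 + 0.4935)² / 0.002025 = 231.7, so 232. Then 232/0.92 = 252.2, so 253. Both reproduce.

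**The Wilson rule with every outcome known (exact binomial).**
- n = 232: at least 217 free of failure; level 4.0%, power 79.0%.
- n = 253: at least 236; level 4.5%, power 83.9%.

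**8% loss among 253 treated.** Let λ = −ln(π)/5 and μ = −ln(0.92)/5. The share with an observed failure is F = λ/(λ+μ)·(1 − e^(−5(λ+μ))). The share followed and free at 5 years is S = 0.92π.
- π = 0.90: F = 0.0960, lost without failure 0.0760, S = 0.8280.
- π = 0.945: F = 0.0528, lost without failure 0.0778, S = 0.8694.

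Expected p under two rules:
- Lost dropped, early failures kept: S/(S+F) = 0.8961 and 0.9428.
- Lost counted as bDFS: 1 − F = 0.9040 and 0.9472.

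A strict completers rule keeps only patients followed for the full 5 years, whether or not they failed earlier, so p stays at π and n is Binomial(253, 0.92).

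| Rule | Level at 90% | Power at 94.5% |
|---|---|---|
| Strict completers | 4.5% | 80% |
| Lost dropped, early failures kept | 3.0% | 76% |
| Lost counted as bDFS | 6.8% | 88% |
| Lost counted as failures | <0.1% | 0.1% |

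**Adding deaths without PSA failure (3%, 5%, 10%), treated like losses.**
- Dropped, early failures kept: power 73%, 71%, 65%.
- Counted as bDFS: level 7.9%, 8.6%, 10.8%.
- Strict completers: level about 4.5%; power 80%, 79%, 76%.

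**One data set, different verdicts.** Take 253 treated, 20 lost and 16 failures among the 233 known.
- Lost excluded, 217/233: L = 0.899, not a success.
- Lost counted as bDFS, 237/253: L = 0.907, success.
- Lost counted as failures, 217/253: L = 0.818, not a success.

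**Start date.** If the 11.3 clock is intended but 60 months are counted from enrollment, the period ends up to 90 days before the month-60 visit. That visit has a window of only 2 weeks either way, so a longer gap can remove it. If month 54 were the last visit counted, a true 90% would appear as 0.90^(54/60) = 0.9095. The chance of 236 or more of 253 is then 11.6%. This is an illustration, because the gaps are not given.

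**Kaplan-Meier alternative (simulated, 253 treated, 8% loss, 9.1.4 visits, one-sided 95% log-log Greenwood limit).**
- Nominal visit times: about 4% and 81%. With 10% deaths: about 4%, and power about 78% to 79%.
- Actual dates spread over the ±2-week window, censoring at the last PSA, no PSA after month 60: the mean estimate at a true 90% is about 85%, and power is about 51%. Event-free patients leave the risk set during the month-60 window, so late failures in it meet a shrinking denominator.

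**The case against.** The strongest reply is that the 232/0.92 step already implies completers only, and that this rule gives the stated 5% and 80%. One sentence defining n would close the gap. Replacing the estimator after an interim look is a larger step for about one point of power. Much of this stands: the gain is small and the timing is a real cost. But the inflation is a planning allowance, not an analysis rule. It does not say whether a man who fails early and is then lost stays in, and that choice separates 80% power from 76%.

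A second reply is that death is settled, because 9.4.1 limits the event to PSA failure or salvage. That makes death a non-event but does not say whether the patient stays in n.

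A third is that the level exceeds 5% through missing data only if lost patients count as bDFS. That is correct, and counting them as failures would be severely conservative instead. Section 11.2 also uses 260 subjects rather than 253; with complete data, 260 needs 242 free of failure (level 5.5%, power 87%). The figures here use the stated 253.

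A reader might infer that the sample size is wrong, or that the level is already above 5%. The documents support neither: the sample size reproduces, and no counting rule has been chosen. A reader might also infer that the level rises smoothly with the gap between consent and treatment. The 6-monthly PSA schedule does not support that, since what matters is whether the month-60 visit is counted.

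**Conclusion.** The gap is real. The test is fully specified only when every 5-year status is known, which the plan does not expect. At the planned 8% loss, the rules that drop lost patients but keep early failures, or count them as bDFS, run from 3.0% level with 76% power to 6.8% with 88%. With an assumed 10% deaths as well, power falls to 65% under the dropping rule and the level rises to 10.8% under the counting-as-bDFS rule. These figures assume constant hazards and loss and death unrelated to PSA failure.

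The start-date conflict is a direct contradiction but secondary. If the 11.3 clock is the intended one, the bias favours success; its size cannot be fixed from the documents.

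Two related matters are not part of these figures. Section 2 names both Phoenix and ASTRO without saying which decides success; that needs naming but is not quantified here. Which statistic the interim Z in 11.2 refers to is a separate clarification.

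**What to change.** - **Clock and population.** In 9.4, 11.3 and 11.4.1, count from the first fraction, and let n be the treated patients.
- **Estimator.** Replace x/n with the Kaplan-Meier 5-year bDFS estimate and its one-sided 95% log-log Greenwood lower limit; success if not below 90%.
- **Phoenix dating.** Assign failures and censoring to the nominal scheduled visit, with the month-60 visit and its ±2-week window counted as 60 months. Censor losses, withdrawals and deaths without PSA failure at the last nominal PSA visit. Do not use actual dates.
- **Sensitivity analyses.** Death counted as an event, and the crude proportion with a stated n.
- **Deciding definition.** Name Phoenix or ASTRO in advance. The 94% projection in 1.15 rests on ASTRO results. For ASTRO, section 9.4.1.2 says "Failure date is the midpoint between the dates of the last non-rising PSA and the first PSA rise"; performance under that backdating has not been modelled, and a failure dated before month 60 may be confirmed only by a later PSA.

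**Cost.** SAP wording and standard software. The primary estimator changes after an interim look in a single-group study, so the change must be dated and justified. Censoring assumes loss and death are unrelated to PSA failure. The gain over a written strict completers rule is about 1 to 2 points of power. If the sponsor keeps the proportion, it must still state n, the status of lost and dead patients, one clock and one deciding definition.
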